6. STUDY TREATMENTS

The study treatment names, abbreviations, and ordering to be used in the TFLs are presented in Table 1.

Table 1: Presentation of Study Treatments in TFLs

Study Treatment	Abbreviation	Order in TFLs
200 mg pirtobrutinib reference lot tablets	R	1
200 mg pirtobrutinib test lot tablets	T	2

All TFLs will be based on actual treatments (eg, if subject was assigned to receive reference but was wrongfully dosed with test treatment they would be summarized and listed under test treatment).

The study treatment sequence names, abbreviations, and ordering to be used in the TFLs are presented in [Table 2](#).

Table 2: Presentation of Study Treatment Sequences in TFLs

Study Treatment Sequence	Abbreviation	Order in TFLs
200 mg pirtobrutinib reference lot tablets / 200 mg pirtobrutinib test lot tablets	R/T	1
200 mg pirtobrutinib test lot tablets / 200 mg pirtobrutinib reference lot tablets	T/R	2

The summaries will be based on planned treatment sequences and listings will be based on actual treatment sequences (eg, if subject was assigned to receive reference in Period 1 and test treatment in Period 2 (sequence 'R/T') but was wrongfully dosed with test treatment in Period 1 and discontinued before start of Period 2, they would be summarized under 'R/T' treatment sequence and listed under 'T' treatment sequence).

7. DEFINITIONS OF POPULATIONS

Any protocol deviations, including those due to coronavirus disease 2019 (COVID-19) and related restrictions (see [Section 8.1.1](#)), will be considered prior to database lock for their importance and taken into consideration when assigning subjects to populations.

7.1. All Subjects Population

The all subjects population will include all subjects who signed the ICF and had any study assessment recorded in the database per the protocol.

7.2. Safety Population

The safety population will include all subjects who received at least 1 dose of study treatment (pirtobrutinib). Subjects will be classified into groups based on actual treatment received.

7.3. Pharmacokinetic Population

The PK population will include all subjects who received a dose of study treatment (pirtobrutinib), have at least 1 quantifiable plasma concentration, and for whom at least 1 PK

parameter can be computed. The impact of protocol deviations on the PK population will be evaluated on a case-by-case basis.

8. STATISTICAL METHODOLOGY

8.1. General

Listings will be provided for all data captured in the database. Listings will include all subjects assigned to the all subjects population and include data up to the point of study completion or discontinuation. Subjects are generally considered to have completed the study if they complete the scheduled EOS phone call (rather than ET visit). Any subject who discontinues the study will be identified accordingly in the listings. Summaries and statistical analyses will include the subjects assigned to the relevant population based on data type.

Data analysis will be performed using the SAS® statistical software package Version 9.4 (or higher if a new version is issued during the study).

Analysis Data Model (ADaM) datasets will be prepared using Clinical Data Interchange Standards Consortium (CDISC) ADaM Version 2.1 (or higher if a new version is issued during the study) and CDISC ADaM Implementation Guide Version 1.2 (or higher if a new version is issued during the study). Pinnacle 21 Community Validator Version 2.2.0 (or higher if a new version is issued during the study) will be utilized to ensure compliance with CDISC standards.

For all statistical analyses, the hypothesis testing will be 2-sided and carried out on 0.05 significance level, unless specifically stated otherwise.

Where reference is made to 'valid' data, this refers to non-missing data which meet the predetermined criteria (eg, are not flagged for exclusion).

Where reference is made to 'all calculations', this includes, but is not limited to, summary statistics, statistical analyses, baseline derivation, and changes from baseline.

All figures will be produced on linear-linear or discrete-linear scales, as applicable, unless specifically stated otherwise.

Any protocol deviations and data issues (eg missing data, out of protocol window) that occur during the study, including those due to COVID-19 and related restrictions (see [Section 8.1.1](#)), will be considered prior to database lock for their severity and impact on the analyses.

8.1.1. Handling of Data Quality Issues Such as Missing Data and Protocol Deviations Due to Coronavirus Disease 2019 and Related Restrictions

Due to COVID-19 and related restrictions, there is a high risk for impact to data integrity, with the recognized potential for:

- Missed visits, caused by, for example,:

- Subject unable to travel to site due to restrictions, the need to quarantine, or COVID-19 infection
- Subject unwilling to go to site due to fear of COVID-19 infection
- Site postponing subject's visit due to investigator not being available (eg, if they have been dispatched to hospital handling COVID-19 infections)
- Site unable to replenish supply of investigational product
- Incomplete data entry by sites due to limited resources to support study or no access to source documents or to eCRF
- Outstanding source document verification (SDV) due to sponsor or country restrictions on remote SDV, or no or limited access to site(s) for on-site visits
- Unanswered queries.

Any protocol deviations and data issues (eg missing data, out of protocol window) that occur during the study, including those due to COVID-19 and related restrictions (see [Section 8.1.1](#)), will be considered prior to database lock for their severity and impact on the analyses. If needed, appropriate statistical methods will be applied as a mitigating action (eg, data might be categorized into 2 analysis groups, with and without COVID-19 and related restrictions impact); however, this will exclude any imputations of the missing values. Any mitigating actions will be agreed with Loxo Oncology, Inc. in advance and identified in the CSR.

8.1.2. Calculation of the Summary Statistics

For continuous data the following rules will be applied:

- Missing values will not be imputed, unless specifically stated otherwise.
- Unrounded data will be used in the calculation of summary statistics.
- If the number of subjects with valid observations (n) <3, summary statistics will not be calculated, with the exception of n, minimum, and maximum.
- In general, as early termination data are not associated with any scheduled timepoint, they will be excluded from all calculations of summary statistics. Exceptions may be made where justified.
- Postdose repeats and unscheduled assessments will not be included in calculations of summary statistics.

For categorical data the following rules will be applied:

- For ordered categorical data (eg, AE severity), all categories between the possible minimum and maximum categories will be included, even if n = 0 for a given category.

- For non-ordered categorical data (eg, race), only those categories for which there is at least 1 subject represented will be included; unless specifically stated otherwise.
- Missing values will not be imputed, unless specifically stated otherwise. A ‘missing’ category will be included for any parameter for which information is missing. This will ensure that the population size totals are consistent across different parameters.

8.1.3. Repeat and Unscheduled Readings

For vital signs and 12-lead ECG data only, any predose value recorded in addition to the original value or a postdose value recorded within 15 minutes of the original value will be defined as a repeat value; any postdose value recorded more than 15 minutes after the original value will be defined as an unscheduled value. For all other data types (eg, laboratory parameters), any value recorded in addition to the original value will be defined as an unscheduled value.

The original scheduled value will be used in all calculations post dose. In the event of any repeats or unscheduled measurements taken pre-dose the values will be considered when determining the baseline value.

As unscheduled values are not associated with any scheduled timepoint, they will be excluded from all calculations, with the exception of the baseline derivation (see [Section 8.1.4](#)). Post dose repeats and ET measurements will also be excluded from all calculations with the exception of the baseline derivation (see [Section 8.1.4](#)).

8.1.4. Definitions of Baseline and Change from Baseline

The baseline will be defined as the last value recorded prior to dosing in each period. In general, baseline will be the predose value collected on Day 1 for period 1 and on Day 8 for period 2, respectively. For clinical chemistry, baseline for period 2 will be the value collected on Day 7 in period 1. If the date/time of the value is incomplete or missing, it will be excluded from the baseline calculation, unless the incomplete date/time indicates the value was recorded prior to dosing in each period.

Individual changes from baseline will be calculated by subtracting the individual subject’s baseline value from the value at the postdose timepoint.

The summary statistics for change from baseline will be derived from individual subjects’ values (eg, mean change from baseline will be the mean of the individual changes from baseline for all subjects, rather than difference between the mean value at the postdose timepoint and mean value at baseline).

See [Section 8.1.3](#) for more detail on handling repeat and unscheduled readings in the calculations.

8.2. Subject Disposition and Population Assignment

Subject disposition and population assignment will be listed.

A summary table by treatment sequence will be provided, based on the safety population.

8.3. Screening Demographics and Baseline Characteristics

The screening demographics and baseline characteristics including age, sex, race, ethnicity, height, body weight, and body mass index will be listed.

A summary table by treatment sequence will be provided, based on the safety population.

8.4. Prior and Concomitant Medication

Prior medication will be defined as medication that ends prior to the first dose. Concomitant medication will be defined as medication that starts during or after the first dose or starts but does not end prior to the first dose.

Prior and concomitant medications will be coded using the World Health Organization Drug Dictionary (WHODrug) Global, Format B3, Version September 2021 (or later if a new version is issued during the study; see the data management plan [DMP] for more details). Prior and concomitant medications will be listed.

8.5. Pharmacokinetic Assessments

8.5.1. Pharmacokinetic Analysis

The following PK parameters will be determined where possible from the plasma concentrations of pirtobrutinib using noncompartmental methods in validated software program Phoenix WinNonlin (Certara, Version 8.1 or higher):

Parameter	Units ^a	Definition
AUC _{0-t}	h*ng/mL	area under the concentration-time curve from hour 0 to the time of the last quantifiable concentration (t _{last}) ^b
AUC ₀₋₂₄	h*ng/mL	area under the concentration-time curve from hour 0 to 24 hours postdose
AUC _{0-inf}	h*ng/mL	area under the concentration-time curve from hour 0 extrapolated to infinity ^c
%AUC _{extrap}	%	percentage of AUC _{0-inf} due to extrapolation from the last quantifiable concentration to infinity
C _{max}	ng/mL	maximum observed concentration
t _{max}	h	time of the maximum observed concentration
t _{1/2}	h	apparent terminal elimination half-life
CL/F	L/h	apparent systemic clearance
MRT _{inf}	h	mean residence time (based on AUC _{0-inf})
V _{z/F}	L	apparent volume of distribution during the terminal phase

^a Units are based on concentration units (provided by the bioanalytical lab or preferred units for presentation of PK parameters) and dose units used in the study.

^b The AUC will be calculated using the linear trapezoidal rule for increasing and decreasing concentrations.

^c Based on the last observed quantifiable concentration.

Additional PK parameters may be determined where appropriate.

The PK analysis will be carried out where possible using actual blood sampling times postdose. If an actual time is missing, the sample concentration result will be treated as missing unless there is scientific justification to include the result using the nominal time.

The parameters C_{max} and t_{max} will be obtained directly from the concentration-time profiles. If C_{max} occurs at more than 1 timepoint, t_{max} will be assigned to the first occurrence of C_{max} .

8.5.1.1. Criteria for the Calculation of Apparent Terminal Elimination Rate Constant and Half-life

The start of the terminal elimination phase for each subject will be defined by visual inspection and generally will be the first point at which there is no systematic deviation from the log-linear decline in concentrations.

The apparent terminal elimination rate constant (λ_z) will only be calculated when a reliable estimate can be obtained using at least 3 data points, preferably not including C_{max} , and the adjusted coefficient for determination of exponential fit (R^2 -adj) of the regression line is ≥ 0.7 . Parameters requiring λ_z for their calculation (eg, AUC_{0-inf} , $t_{1/2}$, CL/F , and V_z/F) will only be calculated if the R^2 -adj value of the regression line is ≥ 0.7 .

The following regression-related diagnostic PK parameters will be determined, when possible:

Parameter	Units	Definition
λ_z	1/h	apparent terminal elimination rate constant
λ_z Upper	h	end of exponential fit
λ_z Lower	h	start of exponential fit
λ_z N	NA	number of data points included in the log-linear regression
λ_z Span Ratio	NA	time period over which λ_z was determined as a ratio of $t_{1/2}$
R^2 -adj	NA	adjusted coefficient for determination of exponential fit

Where possible, the span of time used in the determination of λ_z (ie, the difference between λ_z Upper and λ_z Lower) should be ≥ 2 half-lives. If the λ_z Span Ratio is < 2 , the robustness of the $t_{1/2}$ values will be discussed in the CSR.

8.5.1.2. Criteria for Calculation and Reporting of Area Under the Concentration-time Curve

The minimum requirement for the calculation of AUC will be the inclusion of at least 3 consecutive concentrations above the lower limit of quantification. If there are only 3 consecutive concentrations, at least 1 should follow C_{max} .

The AUC_{0-inf} values where the percentage extrapolation is less than 30% will be reported. The AUC_{0-inf} values where the percentage extrapolation is greater than 30% will be listed but excluded from descriptive statistics.

If $AUC_{0-\infty}$ cannot be determined reliably for all subjects and/or treatments, an alternative AUC measure, such as AUC to a fixed timepoint or AUC_{0-t} , may be used in the statistical comparison of treatments.

8.5.1.3. Criteria for Handling Concentration Below the Limit of Quantification or Missing Concentrations for Pharmacokinetic Analysis

Plasma concentrations below the limit of quantification (BLQ) will be assigned a value of 0 before the first measurable concentration and thereafter BLQ concentrations will be treated as missing. The following rules apply to the specific situations defined below:

- If an entire concentration-time profile is BLQ, it will be excluded from PK analysis.
- Where 2 or more consecutive concentrations are BLQ at the end of a profile, the profile will be deemed to have terminated and any further quantifiable concentrations will be set to missing for the calculation of the PK parameters, unless they are considered to be a true characteristic of the profile of the drug.
- If a predose plasma concentration is missing, it will be set to 0 by default within Phoenix WinNonlin.

8.5.1.4. Treatment of Outliers in Pharmacokinetic Analysis

If a value is considered to be anomalous due to being inconsistent with the expected PK profile, it may be appropriate to exclude the value from the PK analysis. However, the exclusion of any data must have strong justification and will be documented in the CSR.

Any quantifiable predose concentration value in the first treatment period will be considered anomalous and set to missing for the PK analysis. A missing predose concentration will be set to 0 by default in Phoenix WinNonlin.

If the predose concentration is $>5\%$ of C_{max} in the second treatment period, all PK concentration and parameter data will be excluded from the summary statistics and statistical analysis for that period.

8.5.2. Presentation of Pharmacokinetic Data

All PK concentrations and parameters will be listed.

Summary tables, arithmetic mean (+ standard deviation [SD]) figures, overlaying individual figures by treatment, and individual figures with treatments overlaid will be provided for plasma PK concentrations. All figures will be produced on both linear-linear and linear-logarithmic scales. The $\pm SD$ bars will only be displayed on the linear-linear scale.

Summary tables by treatment will be provided for all PK parameters, with the exception of diagnostic regression-related PK parameters. Summary statistics (n, Mean, SD, CV, minimum, median, maximum, geometric mean [Geom Mean] and geometric CV [Geom CV]) will be calculated for plasma pirtobrutinib PK parameters. Individual values and geometric means of PK parameters will be plotted.

A subject may be excluded from the PK summary statistics and statistical analysis when the subject has an AE of vomiting that occurs on or before 2 times the median t_{max} .

Individual concentrations deemed to be anomalous will be flagged in the listings and excluded from the summary statistics.

For plasma concentration data the following rules will apply:

- Values that are BLQ will be set to 0 for the calculation of summary statistics.
- Arithmetic mean or median values that are BLQ will be presented as 0.
- If any BLQ results (treated as 0) are in a series of summarized data, geometric mean and CV of geometric mean will be reported as not calculated.

For PK parameters the following rule will apply:

- Geometric mean and CV will not be calculated for t_{max} .

8.5.3. Pharmacokinetic Statistical Methodology

A statistical analysis will be conducted to investigate the relative bioavailability of 200 mg pirtobrutinib test lot tablets (test treatment) versus 200 mg pirtobrutinib reference lot tablets (reference treatment).

The hypothesis testing will be 2-sided and carried out on 0.1 significance level.

The natural log (ln)-transformed⁴ AUC_{0-t} , AUC_{0-inf} , and C_{max} (only for plasma pirtobrutinib) will be analyzed using a mixed model.⁵ The model will include planned treatment sequence, period, and actual treatment as fixed effects, and subject within planned treatment sequence as a random effect.

For each PK parameter separately, the least squares mean (LSM) for each treatment, difference in LSMs between the test and reference treatments, and corresponding 90% CI will be calculated; these values will then be back-transformed to give the geometric least square mean (GLSM), geometric mean ratio (GMR), and corresponding 90% CI.

It will be concluded that the test treatment is bioequivalent to the reference treatment if, for all tested PK parameters, the 90% CI for GMR is completely contained within the predefined interval of (80.00%, 125.00%).⁶ This procedure is equivalent to Schuirmann's⁷ two one-sided tests at the 0.05 level of significance.

Additionally, the pooled estimate (across treatments) of the within-subject CV will be calculated, and residual plots will be produced to assess the adequacy of the model(s) fitted.

Examples of the SAS code that will be used are as follows:

Mixed Model Analysis

```
proc mixed data = <data in>;
```

```
by parcat1n parcat1 pkday paramn param;
class trtan aperiod trtseqp usubjid;
model lpk = trtan aperiod trtseqp / cl residual ddfm = kr;
lsmeans trtan / cl pdiff = control('1') alpha = 0.1;
random intercept / subject = usubjid(trtseqp);
ods output lsmeans = <data out>;
ods output diffs = <data out>;
ods output covparms = <data out>;
run;
```

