5.1. Randomization

Subjects will be assigned a unique identification number upon screening. Subjects who complete the study screening assessments and meet all the eligibility criteria will be assigned a unique randomization identification number (in accordance with the requirements in [Section 4.5](#) and the randomization scheme generated by Labcorp Drug Development) prior to the time of the first dose, different from the screening number, and will receive the corresponding product according to the randomization scheme generated by Labcorp Drug Development.

Subjects will receive each treatment (T and R) on 1 occasion. The treatments will be administered on Day 1 (Treatment T or R) and Day 8 (Treatment T or R). The sequences to be used in the randomization will be TR and RT.

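### Does the BY statement with pkday in the SAP's example code break the crossover analysis?

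*SAP*

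**What the plan says.** SAP section 8.5.3 describes the primary model in words: "The model will include planned treatment sequence, period, and actual treatment as fixed effects, and subject within planned treatment sequence as a random effect". The estimates and 90% CIs are to be produced for each PK parameter separately. The text mentions no split by day. It also asks for a within-subject CV pooled across treatments. Protocol section 8.3.2 gives the same model.

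The code that follows is introduced with "Examples of the SAS code that will be used are as follows" and has placeholders for the input and output datasets. Its BY statement is "by parcat1n parcat1 pkday paramn param" and its model statement is "model lpk = trtan aperiod trtseqp / cl residual ddfm = kr". A random intercept for subject nested in planned sequence is also fitted.

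On day numbering, SAP section 8.1.4 says "baseline will be the predose value collected on Day 1 for period 1 and on Day 8 for period 2". Protocol section 5.1 (Randomization) likewise places the two treatments on Day 1 and Day 8. `pkday` is not defined in either document.

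**The concern.** A BY statement fits the model afresh in each BY group. The visible text of both documents numbers study days continuously, so a variable called `pkday` could naturally hold 1 for the first profile and 8 for the second. It would then be a second copy of period, and each fit would see only half of the crossover.

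Within Day 1, every TR subject is on T and every RT subject is on R; within Day 8 the reverse holds. With sequence in the model, nothing is left from which to estimate T minus R. The ratio, its 90% CI and the within-subject CV, which together are the primary result, would all be lost. An analyst who repaired this by dropping sequence would be left with a between-subject comparison in each period and would give up the precision the crossover was chosen for. Each treatment is given once, with one profile per period, so it is hard to see what `pkday` adds.

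**Working it through.** **Inputs.** 28 evaluable subjects, 14 per sequence, within-subject CV 25%, true ratio 1.05 or 0.95, limits 80.00% to 125.00% (protocol section 8.1); two one-sided tests at 0.05 (SAP section 8.5.3); sequences TR and RT.

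**The plan's own power figure.** Within-subject SD on the log scale: √ln(1 + 0.25²) = √ln(1.0625) = 0.246. Standard error of the T−R difference: 0.246 × √(2/28) = 0.0658, with 28 − 2 = 26 degrees of freedom. Exact power of the two one-sided tests is 81.6% at 1.05 and 80.7% at 0.95. The stated 81% is reproduced within rounding.

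**Both periods in one fit** (`pkday` removed, or equal in both periods). There are 56 records and the fixed-effects design (intercept, treatment, period, sequence) has rank 4. T−R and the treatment least squares means are estimable. The half-width of the 90% CI is 0.112 on the log scale, so the CI is the estimated ratio multiplied and divided by exp(0.112) = 1.119. The power above applies.

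**`pkday` equal to 1 and 8.** Each BY group has 28 records, one per subject, and a single period. Subjects by sequence and treatment:

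| | R | T |
|---|---|---|
| Day 1, RT | 14 | 0 |
| Day 1, TR | 0 | 14 |
| Day 8, RT | 0 | 14 |
| Day 8, TR | 14 | 0 |

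The rank in each group is 2. T−R and the treatment least squares means are not estimable. With one record per subject, the subject and residual variances cannot be separated.

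**Dropping sequence as a repair.** The between-subject variance is not in the documents, so its CV is an assumption here. With σw² and σb² the within- and between-subject variances on the log scale, the ratio of the parallel-group standard error to the crossover standard error is √[(σw² + σb²)(2/14)] ÷ √[(σw²/2)(2/14)] = √[2(σw² + σb²)/σw²]. With σw² = ln(1.0625) = 0.0606, between-subject CVs of 25%, 35% and 50% give 2.0, 2.4 and 3.1.

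**Which reading fits the code.** Under the 1 and 8 coding, `aperiod` would have one level in every fit and the random intercept would have one record per subject. Both terms would be pointless. They make sense only if each BY group holds both periods. Period also has its own variable already, so there is no reason for a second one to carry it.

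**The case for a change.** The strongest case for a change is that this is the only code given for the primary analysis, that the visible text numbers days continuously, and that a programmer should not have to guess. Removing the word costs nothing. Nor is the failure certain to be complete: SAP section 6 allows for a subject receiving the wrong treatment. If one subject were mis-dosed in period 1, the Day 1 fit would have rank 3 and T−R would become formally estimable, but only through that subject.

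The aliasing stands in full if `pkday` is 1 and 8, and the mis-dosing case is real. Neither shows that the planned analysis is wrong. Variable coding belongs to the analysis datasets and the separate table shells, which are not part of these documents. A row of the protocol's Appendix 4 next to the dosing row is blacked out, so the absence of another day label in the visible text proves little. Even with a mis-dosed subject, the output would come in one block per day instead of one result per parameter, which conflicts with the SAP text on sight.

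The standard error ratio of 2.0 to 3.1 needs a further step: an analyst would have to remove sequence from a model whose text requires it. SAP section 1 requires substantial deviations to be agreed with the sponsor and identified in the study report. The ratio therefore measures a departure from the SAP and says nothing against the SAP itself.

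**Conclusion.** No change to the plan follows. The concern is right about one possible coding of an undefined variable, but the documents do not establish that coding, and the model terms in the same block speak against it. The text in SAP section 8.5.3 and protocol section 8.3.2 fully determines the estimator, and the code is offered as an example of it. An analyst following that text fits both periods together and obtains an estimable T−R difference with the stated power (81.6% at a ratio of 1.05, 80.7% at 0.95).

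If `pkday` were set to the dosing day by mistake, the usual outcome would be no treatment estimate at all, not a quietly biased one. Protocol section 8.5 provides for independent peer review of all tables, figures and listings, and for review of the drafts at a dry run, where a missing primary result would be noticed. Deleting the variable, or giving it the same value in both periods, would tidy the code but would change no result. This conclusion assumes that the written model takes precedence over the example code where the two could differ, and that the peer review and dry run take place as described.
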